5.5 EXPLORATORY ENDPOINT ANALYSIS

The exploratory efficacy objective for this study is to evaluate the efficacy of GDC-9545 compared with physician's choice of endocrine monotherapy on the basis of the following endpoints:

- Mean scores and mean change from baseline in functional scores (physical, role, cognitive, emotional, and social), GHS/QoL, and disease- and treatment-related symptom scores,

This exploratory analysis will be based on PRO-evaluable population, which will include all randomized patients who have a baseline and at least one post-baseline assessment. Summary statistics (mean, standard deviation, median, 25th and 75th percentiles, and

range) of scores will be reported for the "worst pain" item of the BPI-SF, as well as all linear transformed scores for scales (symptoms, functional domains, and GHS/QoL) of the QLQ-C30 and QLQ-BR23 questionnaires for each assessment time point. The mean change of the linear transformed scores from baseline (and 95% CI using the normal approximation) will also be analyzed for each treatment arm. Line charts depicting the mean and mean changes from the baseline assessment (and 95% CIs) of items and scales over time will be provided for each treatment arm.

In the event of incomplete data for all questionnaire scales, if more than 50% of the constituent items are completed, a prorated score will be computed consistent with the scoring manuals and validation papers (see protocol). For scales with less than 50% of the items completed, the scale will be considered as missing in accordance with the EORTC scoring manual guidelines.

PRO completion, compliance rates, and reasons for missing data will be summarized at each time point by treatment arm for each measure in ITT population. The compliance rate will be based on the total number of patients expected to complete the questionnaire at a particular time point.

5.6 SAFETY ANALYSES

The safety analysis population will consist of all patients who received at least one dose of study drug (GDC-9545 or physician's choice of endocrine monotherapy), with patients grouped according to treatment received.

5.6.1 Extent of Exposure

Drug exposure will be summarized using descriptive statistics, including duration of treatment, cumulative dose, and dose intensity.

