Eligible patients will be randomly assigned in a 1:1 ratio to either an experimental arm to receive GDC-9545 or a control arm to receive physician's choice of endocrine monotherapy (as defined in Section 2). Patients will be stratified by site of disease, assessed locally (visceral [any lung and/or liver involvement] vs. non-visceral [absence of any lung and/or liver involvement]), prior treatment with CDK4/6 inhibitor (yes vs. no); and prior treatment with fulvestrant (yes vs. no).

The number of premenopausal/perimenopausal patients and male patients enrolled will be limited to approximately 20% of the study population. The cap of 20% has been chosen to ensure that the mix of patients in this study approximates global clinical practice patterns.

Patients will receive open-label study drug as follows, beginning on Day 1 of Cycle 1:

- Patients in the experimental arm will receive GDC-9545 30 mg taken orally (PO) QD on Days 1–28 of each 28-day cycle
- Patients in the control arm will receive physician's choice of endocrine monotherapy in accordance with local prescribing guidelines

In addition, premenopausal/perimenopausal patients and male patients in both arms will receive an LHRH agonist. To minimize the potential of exposure to the medication decreasing to sub-therapeutic levels towards the end of the treatment cycle, monthly injections of LHRH agonist are preferred and to be synchronized with Day 1 of each 28-day cycle (or according to clinical practice for the selected agent).

Crossover between treatment arms will not be permitted in the study.

Patients who withdraw from the study or who discontinue study treatment will not be replaced. However, patients who withdraw from the study after screening, but before randomization, will be replaced.

Patients may continue to receive study treatment until disease progression or unacceptable toxicity, whichever occurs first. An exception will be made for patients who have developed isolated brain metastases that are treatable with radiation, provided the patients have experienced a PR, CR, or SD for ≥ 24 weeks. These patients will be allowed to continue to receive study treatment until systemic progression of disease and/or further progression in the brain.

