6.1 DETERMINATION OF SAMPLE SIZE

Approximately 300 patients will be enrolled and randomized in a 1:1 ratio to receive either GDC-9545 (experimental arm) or physician's choice of endocrine monotherapy (control arm). The sample size is determined by the primary endpoint, investigator-assessed PFS, comparing the two treatment arms.

The primary analysis of PFS will be conducted when approximately 166 PFS events from both arms are observed. The 166 PFS events allow for 80% power to detect an improvement in median PFS from 5.5 months to approximately 8.5 months (hazard ratio=0.647) at the 5% (two-sided) level of significance. The

largest hazard ratio determined to be statistically significant at the 5% level will be approximately 0.738 (with median improvement in PFS from 5.5 to 7.5 months).

The enrollment duration is projected to be approximately 15 months after randomization of the first patient. For both the GDC-9545 and control arms, an annual loss to follow-up rate of 10% is assumed. On that basis, it is projected that the primary PFS analysis will occur approximately 18 months after the first patient is enrolled.

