3. SAMPLE SIZE DETERMINATION

The primary analysis of PFS will be conducted when approximately 166 PFS events from both arms are observed. The study is designed with 80% power at the 5% (two-sided) level of significance to detect hazard ratio of 0.647, which corresponds to an improvement in median PFS from 5.5 months to approximately 8.5 months. The largest hazard ratio (smallest effect size, minimal detectable difference, MDD) determined to be statistically significant at the 5% level will be approximately 0.738 (which corresponds to median improvement in PFS from 5.5 to 7.5 months).

Approximately 300 patients will be enrolled and randomized in a 1:1 ratio to receive either GDC-9545 (experimental arm) or physician's choice of endocrine monotherapy (control arm). Given assumptions on recruitment intensity (see [Table 2](#) below); the enrollment is projected to finish approximately 15 months after randomization of the first patient. For both the GDC-9545 and control arms, an annual loss to follow-up rate of 10% is assumed. On that basis, it is projected that the primary PFS analysis will occur approximately 18 months after the first patient is enrolled.

Table 2: Recruitment intensity

	Recruitment month from ramp-up to peak														
	1	2	3	4	5	6	7	8	9	10	11	12	13	14	15
Participants per month	1	4	9	14	19	23	26	29	28	29	28	29	28	29	4

Sample Size for the China Subpopulation

This study will initially enroll approximately 300 participants across all sites during the global enrollment phase. After completion of the global enrollment phase, additional participants may be enrolled in an extended China enrollment phase at sites in mainland China and/or Taiwan.

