5.6.2 Adverse Events

Adverse events will be mapped to MedDRA thesaurus terms and appropriate MedDRA hierarchy. Adverse event severity will be graded according to NCI CTCAE v5.0. Multiple occurrences of the same event will be counted once at the maximum severity.

The frequency, nature, and severity of treatment-emergent adverse events, adverse events leading to death, adverse events leading to study drug discontinuation, serious adverse events, and adverse events of special interest will be summarized by treatment arm. All deaths will be summarized. Treatment-emergent adverse events are defined as adverse events that occur after the first dose of study treatment.

Relevant vital signs will be presented using summary statistics by treatment received. Selected laboratory and vital sign data will be summarized by treatment received, and

grade compared with baseline and measurements outside of the normal range will be identified.

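### Adverse events are compared only as crude per-patient percentages, although the design expects longer exposure on GDC-9545; exposure-adjusted rates should be added to SAP 5.6.2

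*SAP*

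**What the plan says.** The safety objective (Protocol 2.2, SAP Table 1) is to evaluate GDC-9545 against physician's choice of endocrine monotherapy, so it is comparative. SAP 5.6.2 summarises the frequency, nature and severity of AEs by arm, with the counting rule "Multiple occurrences of the same event will be counted once at the maximum severity". Protocol 6.5.1 says the same. SAP 5.6.1 covers exposure separately: "Drug exposure will be summarized using descriptive statistics", namely duration, cumulative dose and dose intensity.

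Time on treatment depends on efficacy. Protocol 3.1.1 states: "Patients may continue to receive study treatment until disease progression or unacceptable toxicity, whichever occurs first". Protocol 5.3.1 collects AEs for a further 30 days past the last dose. SAP 3 gives the design effect as a hazard ratio of 0.647, "which corresponds to an improvement in median PFS from 5.5 months to approximately 8.5 months".

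Neither document plans AE rates per patient-year, exposure-adjusted incidence or time to first AE. Other safety data are indexed by time: SAP 5.6.3 summarises laboratory values over time, and SAP 5.6.4 reports PRO-CTCAE and GP5 at each assessment.

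**The concern.** The share of patients with at least one event rises with the time they are watched. If GDC-9545 delays progression as the design assumes, its patients are treated and observed longer. They accumulate more first events even when the monthly hazard is the same in both arms. The crude comparison then mixes toxicity with observation time, and the direction is known: against the more effective arm. Summary tables of treatment duration show that an imbalance exists, but a reader cannot recover time at risk for a first event from them. The reverse error is also open, because a real excess of events could be put down to longer exposure with nothing in the report to test that explanation.

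**Working it through.** **Inputs from the documents.** SAP 3: medians 5.5 and 8.5 months, 166 events, 300 patients 1:1, the monthly recruitment of Table 2, 10% annual loss, cutoff at about month 18. SAP 5.8.1: final OS cutoff at about month 40. Protocol 5.3.1: 30-day AE tail.

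**Assumptions.** The documents give no planning AE rate. I take constant AE hazards λ of 0.02, 0.05, 0.10 and 0.20 per month, equal in both arms. Time to progression is exponential, and treatment ends at progression or loss.

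**Reproducing the plan.** Events = 4(1.960 + 0.842)²/(ln 0.647)² = 165.6, so 166, as stated. The median ratio is 8.5/5.5 = 1.545. With Table 2 accrual and 10% annual loss, the model expects 170 PFS events at month 18 (158 at month 17), which agrees with the plan's timing. The accrual model is therefore a fair basis for what follows.

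**Complete follow-up, no tail.** Progression hazards are ln 2/5.5 = 0.1260 and ln 2/8.5 = 0.0815 per month. Crude incidence = λ/(λ + progression hazard). For λ = 0.10 this is 44.2% versus 55.1%.

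**At a calendar cutoff C.** A patient entering at time e has follow-up F = C − e. The stopping hazard is h = progression hazard + d, with d = −ln(0.9)/12 = 0.0088. Then

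P(first AE) = [λ/(λ + h)] × [1 − exp(−(λ + h)F)],

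averaged over the Table 2 entry times. With a tail τ of 30 days (0.99 months) and F > τ,

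P = 1 − exp(−λτ) + exp(−λτ) × [λ/(λ + h)] × [1 − exp(−(λ + h)(F − τ))].

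For λ = 0.10 at month 18 without the tail, this gives 36.2% versus 41.7%.

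**Artificial gap, GDC-9545 minus control, percentage points:**

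| AE rate per month | Complete follow-up, no tail | Month 18, no tail | Month 18, tail | Month 40, no tail | Month 40, tail |
|---|---|---|---|---|---|
| 0.02 | 6.0 | 1.7 | 1.5 | 4.7 | 4.6 |
| 0.05 | 9.6 | 3.6 | 3.0 | 8.2 | 7.7 |
| 0.10 | 10.8 | 5.5 | 4.4 | 9.8 | 8.9 |
| 0.20 | 9.7 | 6.7 | 5.0 | 9.1 | 7.5 |

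Staggered entry explains the smaller month-18 figures. Mean time on treatment is then about 5.1 versus 6.1 months, a ratio of 1.19 rather than 1.55; by month 40 it is 7.3 versus 10.4 months, a ratio of 1.42. The tail adds the same time to both arms and narrows the gap further.

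**Against the reported results (Protocol 1.2.2.2).** Median PFS was 5.55 versus 5.36 months, with hazard ratio 0.81. At least one AE occurred in 84.7% versus 71.1%, a difference of 13.6 points. Starting from 71.1%, scaling exposure by the medians gives 1 − (1 − 0.711)^(5.55/5.36) − 0.711 = 1.2 points. Scaling by the hazard ratio gives 0.711/(0.711 + 0.81 × 0.289) − 0.711 = 4.1 points. Both are rough.

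**The case against.** The strongest reply has four parts.

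- **Size.** A reader might infer from the 55% longer median PFS that AE percentages would differ by 6 to 11 points. The documents do not support that for the primary analysis. It needs every patient followed to progression and no 30-day tail, whereas SAP 3 plans 15 months of accrual, 10% annual loss and a month-18 cutoff. This objection stands, and the smaller figures are the ones to use.
- **Scope.** A reader might also infer that the whole safety comparison is crude incidence. It is not: laboratory values, PRO-CTCAE and GP5 are summarised over time, and exposure is tabulated. This also stands, and limits the point to the AE tables. Those other summaries do not supply adjusted rates for serious, Grade 3 or higher, or special-interest AEs.
- **Realised data.** The reported medians were nearly equal, so the assumed imbalance did not arise to the planned degree. It would be wrong to read the observed 13.6-point difference as mainly an exposure effect, since rough scaling accounts for 1 to 4 points of it. That weakens the practical penalty but not the case for adjusted rates, which would have settled the question directly. A plan should also be sound under its own design assumptions.
- **Method.** Safety is descriptive, with no between-arm test, and person-time rates bring their own constant-hazard assumption. They can dilute early-onset events in the longer-exposed arm. This is fair, and is why the rates belong beside the percentages and not in place of them.

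**Conclusion.** The point holds as a minor, directional omission. SAP 5.6.2 and Protocol 6.5.1 compare AEs by crude per-patient incidence, and exposure is described but not used. Under the design alternative of 5.5 versus 8.5 months and equal constant AE hazards, GDC-9545 would look worse by about 1.5 to 7 points at month 18 (1.5 to 5 with the tail) and by about 5 to 9 points at month 40 with the tail. The ceiling is about 11 points, with complete follow-up and no tail.

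These sizes rest on AE rates the documents do not give, on a constant AE hazard, and on treatment ending only at progression or loss. If events cluster early, the gap is smaller. The direction does not change at any cutoff examined, and the gap at month 40 exceeds that at month 18. Nothing here touches the primary PFS analysis, the sample size or any hypothesis test.

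**What to change.** In SAP 5.6.2, keep the crude percentages and add exposure-adjusted incidence rates beside them: patients with a first event per 100 patient-years at risk. At-risk time should run from first dose to the earliest of the first event, 30 days after the last dose, or the data cutoff. Give between-arm rate differences with 95% CIs for all AEs, Grade 3 or higher AEs, serious AEs and AEs of special interest. State that the rates assume a roughly constant hazard, can dilute early-onset events, and are to be read with the percentages.

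The cost is a few extra table columns from dosing and AE dates already collected. Because the current protocol already reports the primary results, any such rates produced for that cutoff under an amended SAP should be labelled as added afterwards.

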5.6.2 Adverse Events

Adverse events will be mapped to MedDRA thesaurus terms and appropriate MedDRA hierarchy. Adverse event severity will be graded according to NCI CTCAE v5.0. Multiple occurrences of the same event will be counted once at the maximum severity.

The frequency, nature, and severity of treatment-emergent adverse events, adverse events leading to death, adverse events leading to study drug discontinuation, serious adverse events, and adverse events of special interest will be summarized by treatment arm. All deaths will be summarized. Treatment-emergent adverse events are defined as adverse events that occur after the first dose of study treatment.

Relevant vital signs will be presented using summary statistics by treatment received. Selected laboratory and vital sign data will be summarized by treatment received, and

grade compared with baseline and measurements outside of the normal range will be identified.

5.6.3 Laboratory Data

Relevant laboratory values will be summarized by treatment arm over time, with NCI CTCAE v5.0 Grade 3 and Grade 4 values identified, where appropriate. Summary tables of clinically relevant shifts in NCI CTCAE v5.0 grades (Grades 1, 2) at baseline to the worst post-baseline (Grade ≥ 3) value will be presented.

A Hy's Law analysis will be provided: the finding of an elevated ALT or AST ($> 3x$ upper limit of normal [ULN]) in combination with either an elevated total bilirubin ($> 2x$ ULN) or clinical jaundice in the absence of cholestasis or other causes of hyperbilirubinemia is considered to be an indicator of severe liver injury (as defined by Hy's Law).

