Given that the study drug, GDC-9545, is not expected to increase the risk or severity of COVID-19, no specific SARS-CoV-2 safety management guidelines are deemed necessary, and patients should be treated as per institutional standards of care with decisions for interruptions of study drugs taken by the sites based on the severity of the infection. Please also refer to the guidelines provided for GDC-9545 for the management of non-hematological toxicity in Section 5.1.3.3 and the local labels for other study drugs. Patients with serious infection within 14 days prior to randomization are excluded; however, no testing for SARS-CoV-2 is required. Investigational sites will be specifically trained in the reporting of any occurrences of COVID-19, and the safety of patients will continue to be monitored regularly by both the Sponsor and IMC.

At this time, there is insufficient experience with SARS-CoV-2 vaccines to support concrete recommendations concerning the use of SARS-CoV-2 vaccines in patients receiving GDC-9545 or other endocrine therapies for breast cancer. SARS-CoV-2 vaccines must be given in accordance with the approved/authorized vaccine label and official immunization guidance. The decision of administration of a SARS-CoV-2 vaccine should be individualized based on a patient's SARS-CoV-2 infection/complication risk, the general condition of the patient as well as the epidemiology of COVID-19 in the patient's given area or region.

Based on the data available to date regarding adverse reactions reported in patients receiving SARS-CoV-2 vaccines, the risk of serious or severe overlapping toxicities is low. Based on the mechanism of action and current knowledge, it seems unlikely that GDC-9545 might have an impact on SARS-CoV-2 vaccine efficacy or that mRNA (e.g., Pfizer/ BioNTech BNT162b2, Moderna), inactivated (e.g., Sinopharm, Sinovac, Bharat) replication deficient viral vector (e.g., AstraZeneca/Oxford, Johnson and Johnson, Gamaleya) or protein subunit vaccines (e.g., Anhui Zhifei Longcom, FBRI SRC VB Vector) could impact the safety or efficacy of GDC-9545.

Please check the specific label of any vaccine to ensure compatibility prior to use.

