4.5.7 Laboratory, Biomarker, and Other Biological Samples

Laboratory samples should be drawn according to the schedules of activities (see [Appendix 1](#), [Appendix 2](#), and [Appendix 3](#)). For patients receiving GDC-9545, laboratory samples should be drawn within 72 hours prior to study drug administration and results of the following assessments should be available for review at each clinic visit prior to dosing to inform dosing decisions: complete blood count, total bilirubin, ALP, AST, ALT, creatinine, BUN, and pregnancy test.

Samples for the following laboratory tests will be sent to the study site's local laboratory for analysis:

- Hematology: WBC count, RBC count, hemoglobin, hematocrit, platelet count, and differential count (neutrophils, eosinophils, basophils, monocytes, lymphocytes, other cells)
- Chemistry panel (serum or plasma): bicarbonate or total carbon dioxide (if considered standard of care for the region), sodium, potassium, chloride, glucose, BUN or urea, creatinine, total protein, albumin, phosphate, calcium, total and direct bilirubin, ALP, ALT, AST, urate, and LDH
- Pregnancy test
 - All women of childbearing potential will have a serum pregnancy test at screening, within 7 days prior to initiation of study treatment. Urine pregnancy tests will be performed at specified subsequent visits. If a urine pregnancy test is positive, it must be confirmed by a serum pregnancy test.
- Urinalysis, including dipstick (pH, specific gravity, glucose, protein, ketones, blood) and microscopic examination (sediment, RBCs, WBCs, casts, crystals, epithelial cells, bacteria)
- Coagulation: INR (or PT), PTT (or aPTT)
- FSH and estradiol (for premenopausal/perimenopausal patients and female patients aged <60 years)

The following samples will be sent to one or several central laboratories or to the Sponsor or a designee for analysis:

- Plasma samples for PK analysis (GDC-9545 arm only)
- Plasma sample for determination of *ESR1* mutation status
 - Determination of *ESR1* mutation status will be made using the FoundationOne Liquid CDx assay or an assay from an approved regional vendor.
- Blood and plasma samples for exploratory research on biomarkers and biomarker assay development
- Archival or newly collected tumor tissue sample obtained at baseline upon confirmation of enrollment onto the study for exploratory research on biomarkers

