5.1.3.3 Management Guidelines

Guidelines for management of specific adverse events associated with GDC-9545 are outlined in Table 1. Additional guidelines are provided in the subsections below.

Table 1 Guidelines for Management of Patients Who Experience Adverse Events Associated with GDC-9545

Event	Action to Be Taken
Elevation of Hepatic Transaminases:	
General guidance	
• If patient presents with jaundice, coagulopathy, abdominal pain, or other symptoms suggestive of hepatic toxicity, perform liver function tests with additional evaluation per institutional guidelines.• If hepatic enzymes are elevated with no obvious malignant cause found, consult with hepatologist.• Treat patient with hepatic enzyme elevation according to local standard of care.
Grade 1 or 2	
• Continue GDC-9545.• Rule out alternative etiologies (e.g., liver metastases, concomitant medications, or biliary obstruction).• Treat patient according to local standard of care.• Initiate close monitoring of LFTs until any abnormalities resolve or are assessed as stable.
Grade 3	
• Withhold GDC-9545.
• Consider consultation with hepatologist. If event resolves to Grade ≤ 1 within 28 days, resume GDC-9545 at full dose, continuing close monitoring of LFTs until any abnormalities resolve or are assessed as stable.• If event does not resolve to Grade ≤ 1 within 28 days, permanently discontinue GDC-9545.
Grade 4 or meets criteria as defined by Hy's Law (see Section 5.3.5.7)	
• Permanently discontinue GDC-9545.• Consult with hepatologist.

Event	Action to Be Taken
Gastrointestinal Events (Nausea, Vomiting, Diarrhea)	
General guidance	
 • Monitor closely for GI symptoms. If patient presents with nausea, vomiting, or diarrhea, manage according to local standard of care, including use of anti-diarrheal agents and supportive care such as hydration and dietary modification as appropriate. • Infectious or alternate etiologies should be ruled out.
Grade 1	
 • Continue GDC-9545.
Grade 2	
 • Manage and treat according to local standard of care • If persistent despite appropriate medical therapy, withhold GDC-9545 until resolution to Grade 1 or better.

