5.2.3 Adverse Events of Special Interest (Immediately Reportable to the Sponsor)

Adverse events of special interest are required to be reported by the investigator to the Sponsor immediately (i.e., no more than 24 hours after learning of the event; see Section 5.4.2 for reporting instructions). Adverse events of special interest for this study are as follows:

- Cases of potential drug-induced liver injury that include an elevated ALT or AST in combination with either an elevated bilirubin or clinical jaundice, as defined by Hy's Law (see Section 5.3.5.7)
- Suspected transmission of an infectious agent by the study drug, as defined below
 - Any organism, virus, or infectious particle (e.g., prion protein transmitting transmissible spongiform encephalopathy), pathogenic or non-pathogenic, is considered an infectious agent. A transmission of an infectious agent may be suspected from clinical symptoms or laboratory findings that indicate an infection in a patient exposed to a medicinal product. This term applies only when a contamination of the study drug is suspected.
- Grade ≥ 3 hepatitis or elevations in AST or ALT
- Grade ≥ 3 acute kidney injury, creatinine increase, or renal toxicity
- Grade ≥ 2 bradycardia
- Grade ≥ 2 thromboembolism

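### Protocol-mandated repeat liver testing applies only to the GDC-9545 arm, and the by-arm Grade 3 or higher AST/ALT summaries are not restricted to scheduled samples, so they may record more events on GDC-9545 at equal true risk

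*SAP*

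**What the plan says.** **Scheduled testing.** Protocol Appendix 1 sets the chemistry panel, which includes ALT, AST and bilirubin, at screening, on Day 1 of every 28-day cycle and at the treatment discontinuation visit. It makes no distinction between arms.

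**Extra testing.** Protocol 5.1.3.3 states: "Guidelines for management of specific adverse events associated with GDC-9545 are outlined in Table 1". The Grade 1 or 2 row for hepatic transaminases instructs sites: "Initiate close monitoring of LFTs until any abnormalities resolve or are assessed as stable". No interval is given. The Grade 3 row asks for close monitoring to continue when the drug is resumed.

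**Control arm.** There is no corresponding liver-test rule. Protocol 4.3.2.2 refers control dosing to local prescribing information. The COVID-19 text in Protocol 1.3 points to the "guidelines provided for GDC-9545 for the management of non-hematological toxicity in Section 5.1.3.3 and the local labels for other study drugs". Protocol 5.5.1 requires every adverse event, in either arm, to be followed until it resolves or is stable, but names no test frequency. Protocol 5.3.5.5 makes clear that a laboratory abnormality is not automatically an adverse event.

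**Analysis.** SAP 5.6.3 plans by-arm laboratory summaries and "Summary tables of clinically relevant shifts in NCI CTCAE v5.0 grades (Grades 1, 2) at baseline to the worst post-baseline" value of Grade 3 or higher. Protocol 5.2.3 lists "Grade ≥ 3 hepatitis or elevations in AST or ALT" as a special-interest event, and SAP 5.6.2 states that "adverse events of special interest will be summarized by treatment arm". The SAP does not say how unscheduled samples are handled.

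**The concern.** A patient's worst value cannot fall when samples are added. If the protocol adds samples in one arm only, a worst-value table partly compares how hard each arm was looked at. The special-interest event count has the same feature, because a Grade 3 or higher AST or ALT can be reported only if a sample was taken while it was present.

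The safety objective in Protocol 2.2 compares GDC-9545 with physician's choice, and Protocol 5.1.1.6 lists hepatotoxicity as an identified risk. An excess of Grade 3 or higher elevations on GDC-9545 would be read as a drug effect. The planned tables give the reader no means of judging how much of it could come from more frequent testing.

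**Working it through.** The plan gives no figure to reproduce here. The check compares the rules for the two arms and then illustrates the possible size.

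**1. Testing rules side by side**

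| Item | GDC-9545 | Control |
|---|---|---|
| Scheduled chemistry | Every 28 days and at discontinuation | The same |
| After a Grade 1 or 2 elevation | Close monitoring required, interval undefined | No protocol rule; local practice |
| Elevation judged an adverse event | Follow to resolution or stability | The same |
| Grade 3 or higher AST/ALT as special-interest event | Yes | Yes |

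The gap is in the second row. It concerns Grade 1 or 2 elevations that a control site does not treat as adverse events, and any difference in how intensively the arms are retested.

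**2. Which outputs are affected**

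- The shift table is affected. As worded, it covers only patients already at Grade 1 or 2 at baseline. Such patients can be enrolled, since Protocol 4.1.1 admits AST and ALT up to 3 x ULN, or 5 x ULN with liver metastases.
- The special-interest event count is affected whatever the baseline grade.
- The SAP 5.6.3 summaries of values over time are not worst-value summaries and are not the main issue.

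**3. Size under assumed inputs**

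The documents give neither the monitoring interval nor how long elevations last. Let L be the days spent at Grade 3 or higher, w the days between draws, and q the share of GDC-9545 episodes already under close monitoring when Grade 3 begins. With draws at a random phase:

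- P(detect) = min(1, L/w)
- Control, scheduled draws only: min(1, L/28)
- GDC-9545: q x min(1, L/w) + (1 - q) x min(1, L/28)

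With q = 0.5 and w assumed to be 7 or 14 days:

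| L (days) | Control | GDC-9545, w = 14 | GDC-9545, w = 7 | Ratio |
|---|---|---|---|---|
| 7 | 0.25 | 0.5 x 0.5 + 0.5 x 0.25 = 0.375 | 0.5 x 1 + 0.5 x 0.25 = 0.625 | 1.5 to 2.5 |
| 14 | 0.50 | 0.5 x 1 + 0.5 x 0.5 = 0.75 | 0.75 | 1.5 |
| 21 | 0.75 | 0.5 x 1 + 0.5 x 0.75 = 0.875 | 0.875 | 1.17 |
| 28 or more | 1.00 | 1.00 | 1.00 | 1.0 |

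Across q = 0 to 1 the ratio runs from 1.0 to 4.0. The upper end is q = 1, L = 7, w = 7: 1/0.25.

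**4. If control sites also retest**

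Let r be the share of control episodes retested at the same interval. If r = q, the ratio is 1.0. If r = 0.25, q = 0.5 and L = 14, control detection is 0.25 x 1 + 0.75 x 0.5 = 0.625, and the ratio falls from 1.5 to 0.75/0.625 = 1.2.

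**5. In patients**

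Protocol 6.1 gives about 300 patients randomized 1:1, so about 150 per arm. With an assumed true risk of 5% there are 150 x 0.05 = 7.5 episodes per arm. For L = 14, q = 0.5 and no control retesting, about 7.5 x 0.75 = 5.6 would be recorded on GDC-9545 and 7.5 x 0.50 = 3.8 on control. At a true risk of 2% (3 episodes) the figures are 2.3 and 1.5. At 10% (15 episodes) they are 11.3 and 7.5.

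**The case against.** The strongest reply is that control patients are not left unwatched. A clinically significant or symptomatic elevation, or one that changes treatment, must be reported as an adverse event in either arm (Protocol 5.3.5.5) and then followed (Protocol 5.5.1), which implies repeat tests. Hy's Law reporting (Protocol 5.3.5.7) also covers both arms. This stands. A reader might infer that control patients get scheduled draws only, and the documents do not support that. They support only the absence of a mandated liver-test rule after mild elevations.

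Three further points limit the concern:

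- The Table 1 monitoring that continues after Grade 3 does not affect first detection, because the event is already recorded. Only the Grade 1 or 2 instruction matters.
- Protocol 4.5.7 says: "For patients receiving GDC-9545, laboratory samples should be drawn within 72 hours prior to study drug administration". This might be read as extra testing on GDC-9545, but it governs the timing of samples and adds none.
- The summaries are descriptive, with no test specified. Protocol 5.1.1.6 reports few Grade 3 events. The distortion runs against the experimental drug, so it would not hide an excess of harm.

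These points lower the priority of the issue. They do not remove the difference in testing rules or help a reader interpret an imbalance.

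**Conclusion.** The point holds as a possible ascertainment difference in descriptive safety tables. The difference in testing rules is in the documents, and so is its direction: at equal true liver effects, the added sampling can only leave unchanged or raise the worst grade recorded on GDC-9545. Whether a visible difference results cannot be derived. It depends on the undefined monitoring interval, how long elevations last and what control sites do locally. It is nil for elevations sustained over a full cycle or where control sites retest similarly. It could be substantial for short peaks between monthly draws.

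A reader might infer that Grade 3 or higher elevations definitely are found more completely on GDC-9545, or that a particular percentage is missed on control. The documents support neither, and the figures above are illustrations only.

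The argument also assumes that unscheduled local results reach the study database. If they do not, the laboratory tables are less affected, but the event count still is. The primary endpoint is untouched, and this is a low-cost improvement. Protocol 1.2.2.2 already reports the primary analysis, so the change would serve later safety reporting.

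**What to change.** Keep the all-sample worst-value tables, the special-interest event table and the Hy's Law analysis as the main safety displays. Beside them, add:

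- **SAP 5.6.3:** by-arm AST/ALT worst-grade and shift tables restricted to protocol-scheduled post-baseline samples (Day 1 of each cycle and the discontinuation visit), labelled supportive.
- **SAP 5.6.2:** next to the AST/ALT special-interest event count, the number of patients by arm with Grade 3 or higher AST or ALT on scheduled samples.
- **Either section:** the number of scheduled and unscheduled liver tests per patient by arm, and a sentence saying how unscheduled samples are treated in each table.

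The cost is SAP wording and one extra set of tables from data already collected, provided unscheduled local results are entered. The drawback is that scheduled-only tables miss some true peaks in both arms, so they must not replace the all-sample tables. No change to the clinical monitoring rule is proposed.
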